8.3 Sample size calculations for immunogenicity (Part B)

Immunogenicity sample size calculations allow for a 10% rate of missing immunogenicity data at Months 2.5 and 6.5 ($n = 18$ for analysis) and 15% rate of missing immunogenicity data at Months 12 and 18 ($n = 17$ for analysis).

The first goal is to evaluate immune response rates based on data from the primary TZM-bl neutralizing antibody assay among vaccinees. The precision with which the true response rate can be estimated from the observed data depends on the true underlying response rate and the sample size. Two-sided 95% confidence intervals for the response rate based on observing a particular response rate among vaccinees is shown in Table 4. Calculations are done using the score test method [1].

Table 4: Two-sided 95% confidence intervals for the true response rate based on observing a particular response rate among vaccinees ($n = 18$)

No. of responses	Observed response rate (%)	95% confidence interval
4/18	22.2	(9.0, 45.2)
6/18	33.3	(16.3, 56.3)

8/18	44.4	(24.6, 66.3)
10/18	55.6	(33.7, 75.4)
12/18	66.7	(43.7, 83.7)
14/18	77.8	(54.8, 91.0)
15/18	83.3	(60.8, 94.2)
16/18	88.9	(67.2, 96.9)
17/18	94.4	(74.2, 99.0)

As shown in Table 5, there is limited power for a formal comparison of immunogenicity response rates between vaccine arms of size $n = 20$. For either 80% or 90% power, the sizes of differences that the trial is powered to detect are large. These calculations use a Fisher's exact 2-sided test with a Type I error rate of 0.05. However, the study is adequately powered to detect the differences seen in the CAVD 641 study in rhesus macaques by [name]. Rates of autologous tier 2 neutralizing antibody responses at week 26 (the peak timepoint) were compared between arms with Alum-3M-052 or GLA-LSQ adjuvant, both with BG505-SOSIP protein. The large difference in response rates – 50% vs. 100% – could be detected with 97% power.

Table 5: Power for comparison of response rates between 2 arms (n1 = 18, n2 = 18)

True response rate Arm 1 (%)	Minimum true response rate in Arm 2 in order to detect a difference	
	80% power	90% power
10	58	65
20	71	77
30	81	87
40	89	94
50	95	99

Power for comparing the magnitude of immune responses between pairs of arms with different adjuvants is first calculated using binding antibody data from the HEPLISAV study. Engerix, an HBV vaccine formulated with alum, was compared to HEPLISAV, the same HBV vaccine formulated with CpG 1018. With $n = 18$ vaccinees per arm, the current study has 100% power to detect the difference in geometric mean immune response seen in the HEPLISAV study at Week 28 (the peak timepoint) (79.7 mIU/mL vs. 206.1 mIU/mL), assuming based on the HEPLISAV study that the group with higher geometric mean has a smaller standard deviation (51.38 mIU/mL vs. 6.04 mIU/mL), using a 0.025-level one-sided Wilcoxon rank sum test. In addition, power is also 100% for detecting the difference seen between adjuvants at Week 52 (the durability timepoint), based on the HEPLISAV data (geometric means 19.0 vs. 131.0 mIU/mL and standard deviations 34.57 vs. 6.92 mIU/mL).

In addition, “generic” power calculations inform the power of the study to compare immune response magnitudes between arms. These presume a continuous immune response, transformed to a 1-standard deviation scale, and a mean shift in scaled immune response between arms. Table 6 shows the power for comparing immune responses between pairs of arms with different adjuvants, separately at Months 2.5 and 6.5 ($n = 18$ per arm) and Months 12 or 18 (durability, $n = 17$ per arm) time points. Observe that the study is powered to detect moderate 1-standard deviation differences in immune responses between adjuvants at the early timepoints and 1.1-standard-deviation differences at the durability timepoints.

Table 6: Power for comparing the magnitude of a generic immune response between arms. Immune responses are compared using 0.025-level one-sided Wilcoxon rank sum tests. Continuous immune responses are assumed to follow a normal distribution, transformed to a 1-standard deviation scale, with a mean of zero in one arm and the same standard deviation in the two arms. To allow for missing immunogenicity data, analyses include 17 or 18 subjects in each arm. Power is based on 1000 simulations.

Mean difference between arms (in standard-deviation units)	Power, n = 18 per arm	Power, n = 17 per arm
0.8 SD	63%	61%
0.9 SD	71%	69%
1.0 SD	81%	78%
1.1 SD	85%	85%
1.2 SD	92%	90%
1.3 SD	97%	95%

In addition, the ability of the study to rank and select the adjuvant with the highest immune response at a given timepoint was assessed. Table 7 shows the probability of correctly selecting the adjuvant with the highest mean immune response at Month 6.5, as a function of the mean in the arm with next-lowest mean immune response. Calculations again assume that immune responses have been transformed to the 1-standard deviation scale. The results show that the study is sufficiently sized to correctly rank adjuvant arms, assuming the top two arms have a mean difference of at least 0.5 standard-deviations.

Table 7: Probability of correct ranking. Probability of correctly selecting the adjuvant with the highest mean immune response at Month 6.5, based on a generic standard-deviation-scaled continuous immune response. Probability is shown as a function of the mean immune response in the next-best arm. To allow for missing immunogenicity data, analyses include 18 subjects in each arm. Calculations assume all arms below the best have a mean immune response equal to that of the next-best arm and thus the results are conservative.

Mean difference, best – next-best	Probability of correct ranking
0.1 SD	0.38
0.2 SD	0.52
0.3 SD	0.65
0.4 SD	0.75
0.5 SD	0.82
0.6 SD	0.92

8.4 Sample size calculations for safety (Part C)

The goal of the safety evaluation for Part C of this study is to identify safety concerns associated with administration of 1 or more vaccine regimens studied in Part C. Specifically, for each vaccine arm of Part C (n = 10), there is a 90% chance of observing at least 1 event if the true rate of such an event is 20.6% or more and there is a 90% chance of observing no events if the true rate is 1% or less.

Binomial probabilities of observing 0 events, 1 or more events, and 2 or more events among arms of size 10 are presented in Table 8 for a range of possible true adverse event rates. These calculations provide a more complete picture of the sensitivity of the Part C study design to identify potential safety problems with the two vaccine regimens.

Table 8: Probability of observing 0 event, 1 or more events, and 2 or more events, among arms of size 10, for different true event rates

True event rate (%)	Pr(0/10)	Pr(1+/10)	Pr(2+/10)
1	90.4	9.6	0.4
4	66.5	33.5	5.8
10	34.9	65.1	26.4
20	10.7	89.3	62.4
30	2.8	97.2	85.1

An alternative way of describing the statistical properties of the study design is in terms of the 95% confidence interval (CI) for the true rate of an adverse event based on the observed data. Table 9 shows the 2-sided 95% CIs for the probability of an event based on a particular observed rate. Calculations are done using the score test method [1]. If none of the 10 participants receiving a vaccine regimen experience a safety event, the 95% 2-sided upper confidence bound for the true rate of such events in the total vaccinated population is 27.8%.

Table 9: Two-sided 95% confidence intervals based on observing a particular rate of safety endpoints for arms of size n1 and n2

Observed event rate	95% confidence interval (%)
0/10	(0%, 27.8%)
1/10	(1.8%, 40.4%)
2/10	(5.7%, 51%)

8.5 Sample size calculations for immunogenicity (Part C)

Immunogenicity sample-size calculations allow for a 10% rate of missing immunogenicity data at Month 2.5 and 6.5 (n = 9 for analysis).

The first goal is to evaluate immune response rates based on data from the primary TZM-bl neutralizing antibody assay among vaccinees. The precision with which the true response rate can be estimated from the observed data depends on the true underlying response rate and the sample size. Two-sided 95% CIs for the response rate based on observing a particular rate of responses in the vaccinees is shown in Table 10. Calculations are done using the score test method [1].

Table 10: Two-sided 95% confidence intervals for the true response rate based on observing a particular response rate among vaccinees (n = 9)

No. of responses	Observed response rate (%)	95% confidence interval
1/9	11.1	(2.0, 43.5)
2/9	22.2	(6.3, 54.7)
3/9	33.3	(12.1, 64.6)
4/9	44.4	(18.9, 73.3)
5/9	55.6	(26.7, 81.1)
6/9	66.7	(35.4, 87.9)
7/9	77.8	(45.3, 93.7)
8/9	88.9	(56.5, 98.0)
9/9	100.0	(70.1, 100.0)

As shown in Table 11 and Table 12, there is limited power for a formal comparison of immunogenicity response rates between Parts B and C based on vaccine arms of size n = 10

(Parts A and C) and $n = 20$ (Part B). For either 80% or 90% power, the sizes of differences that the trial is powered to detect are large.

Table 11 Power for comparison of response rates between 2 arms ($n1 = 9$, $n2 = 9$)

True response rate Arm 1 (%)	Minimum true response rate in Arm 2 in order to detect a difference	
	80% power	90% power
10	83	91
20	92	99
30	99	N/A

Table 12 Power for comparison of response rates between 2 arms ($n1 = 9$, $n2 = 18$)

True response rate Arm 1 (%)	Minimum true response rate in Arm 2 in order to detect a difference	
	80% power	90% power
10	72	90
20	83	90
30	91	96
40	92	100

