8.2 Sample size calculations for safety (Part B)

The goal of the safety evaluation for Part B of this study is to identify safety concerns associated with administration of one or more vaccine regimens. Specifically, for each vaccine arm of Part B ($n = 20$), there is a 90% chance of observing at least 1 event if the true rate of such an event is 11% or more; and there is a 90% chance of observing no events if the true rate is 0.5% or less. For the four vaccine arms combined ($n = 80$), there is a 90% chance of observing at least 1 event if the true rate of such an event is 2.9% or more; and there is a 90% chance of observing no events if the true rate is 0.1% or less.

Binomial probabilities of observing 0, 1 or more, and 2 or more events among arms of size 20 and 80 are presented in Table 2 for a range of possible true adverse event rates. These calculations provide a more complete picture of the sensitivity of the Part B study design to identify potential safety problems with the four vaccine regimens.

Table 2: Probability of observing 0 event, 1 or more events, and 2 or more events, among arms of size 20 and 80, for different true event rates

True event rate (%)	Pr(0/20)	Pr(1+/20)	Pr(2+/20)	Pr(0/80)	Pr(1+/80)	Pr(2+/80)
1	81.8	18.2	1.7	44.8	5.2	19.1
4	44.2	55.8	19.0	3.8	96.2	83.5
10	12.2	87.8	60.8	0	100	99.8
20	1.2	98.8	93.1	0	100	100
30	0.1	99.9	99.2	0	100	100

An alternative way of describing the statistical properties of the study design is in terms of the 95% confidence interval for the true rate of an adverse event based on the observed data. Table 3 shows the 2-sided 95% confidence intervals for the probability of an event based on a particular observed rate. Calculations are done using the score test method [1]. If none of the 80 participants receiving a vaccine regimen experience a safety event, the 95% 2-sided upper confidence bound for the true rate of such events in the total vaccinated population is 4.6%. For each individual vaccine arm ($n = 20$), the 2-sided upper confidence bound for this rate is 16.1%.

Table 3: Two-sided 95% confidence intervals based on observing a particular rate of safety endpoints for arms of size n1 and n2

Observed event rate	95% confidence interval (%)
0/20	(0%, 16.1%)
1/20	(0.9%, 23.6%)
2/20	(2.8%, 30.1%)
0/80	(0%, 4.6%)
1/80	(0.2%, 6.7%)
2/80	(0.7%, 8.7%)

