9.4 Immunogenicity analysis

9.4.1 General approach

For the statistical analysis of immunogenicity endpoints, data from enrolled participants will be used according to the initial randomization assignment regardless of how many injections they received. Additional analyses may be performed, limited to participants who received all scheduled injections per protocol. Assay results that are unreliable, from specimens collected outside of the visit window, or from HIV-infected participants postinfection are excluded. Since the exact date of HIV infection is unknown, any assay data from blood draws 4 weeks prior to an infected participant's last seronegative sample and thereafter may be excluded. If an HIV-infected participant does not have a seronegative sample postenrollment, then all data from that participant may be excluded from the analysis.

Data from placebo arms will be pooled across groups ($n = 8$ for analysis in Part B). For analyses of immunogenicity after the second vaccination, data on the 3M-052-AF from Part A (with the maximum tolerated dose of the 3M-052-AF) and Part B will be pooled. Otherwise, analyses of immunogenicity will be performed separately for Part A and Part B participants.

Discrete categorical assay endpoints (e.g., response rates) will be analyzed by tabulating the frequency of positive response for each assay by antigen and treatment arm at each timepoint for which an assessment is performed. Crude response rates will be presented with their corresponding 95% confidence interval estimates calculated using the score test method [1]. Because of the small numbers of control participants in each group, no adjustment will be made to the vaccine arm estimates for the false positive rates (FPRs) in the control arms. Barnard's test will be used to compare the response rates of any 2 vaccine arms, with a significant difference declared if the 2-sided p-value is ≤ 0.05 .

For quantitative assay data (e.g., percentage of positive cells from ICS assay), graphical and tabular summaries of the distributions by antigen, treatment arm, and timepoint will be made. For all primary and secondary immunogenicity endpoints, box plots and plots of estimated reverse cumulative distribution curves (CDFs) will be used for graphical display of all of the study arms. Typically, the results will be shown for each vaccine arm and for the pooled placebo group.

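### Two cells of Table 12 and one of Table 2 are wrong or out of line, and the response-rate power tables do not match the test named for them or the test planned for the analysis

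*SAP*

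**What the plan says.** **Power for comparing response rates.** Section 8.3 introduces Table 5 (18 versus 18) with "These calculations use a Fisher's exact 2-sided test with a Type I error rate of 0.05". Section 8.5 gives Table 11 (9 versus 9) and "Table 12 Power for comparison of response rates between 2 arms" (9 versus 18) in the same layout and names no test. Table 12 prints, for arm-1 rates of 10, 20, 30 and 40%, the pairs 72/90, 83/90, 91/96 and 92/100 (80%/90% power). Section 8.5 concludes that power for a formal comparison is limited and that the detectable differences are large.

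**Planned analysis.** Section 9.4.1 states "Barnard's test will be used to compare the response rates of any 2 vaccine arms", two-sided at 0.05.

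**Safety detection.** Section 8.2 gives "Table 2: Probability of observing 0 event, 1 or more events, and 2 or more events, among arms of size 20 and 80". At a true rate of 1% and n = 80 it prints Pr(0) = 44.8, Pr(1+) = 5.2 and Pr(2+) = 19.1.

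**The concern.** Three things can be seen without calculation.

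- The 90%-power column of Table 12 does not move between arm-1 rates of 10% and 20%, although the detectable arm-2 rate must rise with the arm-1 rate. Its 80%-power column runs 72, 83, 91, 92 and flattens abruptly in the last row.
- In Table 2, Pr(0) and Pr(1+) must add to 100, and Pr(2+) cannot exceed Pr(1+). The 1% row for n = 80 breaks both rules.
- The power section plans with one test and the analysis section uses another.

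Table 12 describes the comparison of a Part C arm with a Part B arm. That includes 3 mcg against 5 mcg of 3M-052-AF, a Part C secondary objective. A reader weighing a null result there would take 10% versus 90% as the smallest contrast detectable with 90% power. Table 2 informs a primary safety objective, and the misprint understates about tenfold the chance of seeing a 1% event among the 80 Part B vaccinees.

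**Working it through.** **Inputs.** Arm sizes 18/18, 9/9 and 9/18 (Tables 5, 11, 12); two-sided alpha 0.05 (Section 8.3). Section 8.5 states no test or alpha, so carrying 0.05 over to Tables 11 and 12 is an assumption.

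**Step 1: find a method that reproduces the printed figures.** Continuity-corrected arcsine approximation:

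power = Φ{ [2·asin√(p2 − 0.5/n2) − 2·asin√(p1 + 0.5/n1)] / √(1/n1 + 1/n2) − 1.96 }

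Each cell is the smallest whole-percent p2 that reaches the target.

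Check on Table 5, 10% row, 80% power (printed 58): p1 + 0.5/18 = 0.1278, so 2·asin√ = 0.7311; √(1/18 + 1/18) = 0.3333.
- p2 = 57%: 2·asin√0.5422 = 1.6553; (1.6553 − 0.7311)/0.3333 − 1.96 = 0.813; power 79.2%.
- p2 = 58%: 2·asin√0.5522 = 1.6754; the same steps give 0.873; power 80.9%. The cell is 58, as printed.

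| Table | Printed (80/90) | Approximation, rounded up | Exact two-sided Fisher | Exact Barnard, rounded up |
|---|---|---|---|---|
| 5, 10% | 58/65 | 58/65 | 56.4/62.8 | 52/58 |
| 5, 20% | 71/77 | 71/77 | 68.2/74.3 | 66/73 |
| 5, 30% | 81/87 | 81/87 | 78.2/84.1 | 77/83 |
| 5, 40% | 89/94 | 89/94 | 87.3/92.0 | 84/89 |
| 5, 50% | 95/99 | 95/99 | 93.8/96.8 | 91/95 |
| 11, 10% | 83/91 | 83/91 | 77.9/85.8 | 74/82 |
| 11, 20% | 92/99 | 92/99 | 88.6/93.8 | 85/91 |
| 11, 30% | 99/N/A | 99/N/A | 95.1/100 | 93/97 |
| 12, 10% | 72/**90** | 72/**80** | 64.1/71.0 | 64/71 |
| 12, 20% | 83/90 | 83/90 | 75.6/82.7 | 75/82 |
| 12, 30% | 91/96 | 91/96 | 85.4/91.0 | 84/90 |
| 12, 40% | **92**/100 | **97**/100 | 92.1/96.0 | 91/96 |

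The approximation matches 10 of 10 cells in Table 5, 6 of 6 in Table 11 and 6 of 8 in Table 12. Fisher and Barnard are by full enumeration of the binomial outcomes; Barnard uses the pooled Z statistic, maximised over 999 nuisance values.

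**Step 2: the two cells that do not match.** Here √(1/9 + 1/18) = 0.4082.

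*10%, 90% power (printed 90).* p1 + 0.5/9 = 0.1556, so 2·asin√ = 0.8108.
- p2 = 79%: 2·asin√0.7622 = 2.1229; (2.1229 − 0.8108)/0.4082 − 1.96 = 1.254; power 89.5%.
- p2 = 80%: 2·asin√0.7722 = 2.1465; the same steps give 1.312; power 90.5%. The cell is 80.
- Every two-sided 0.05 method tried lies between 68.7 and 79.5. At the printed 90, exact Fisher power is 99.6%.

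*40%, 80% power (printed 92).* p1 + 0.5/9 = 0.4556, so 2·asin√ = 1.4818.
- p2 = 92%: 2·asin√0.8922 = 2.4726; (2.4726 − 1.4818)/0.4082 − 1.96 = 0.467; power 68.0%.
- p2 = 96%: 2·asin√0.9322 = 2.6148; 0.815; power 79.3%.
- p2 = 97%: 2·asin√0.9422 = 2.6561; 0.917; power 82.0%. The cell is 97.
- Exact Fisher gives 92.1, so 92 is about right for that test but not for the method behind the other cells.

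**Step 3: named test against printed figures.** Table 5 exceeds exact Fisher by between 95 − 93.8 = 1.2 and 87 − 84.1 = 2.9 points. Under exact Fisher its 80% entries have 83–85% power; under Barnard, 88–91%.

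**Step 4: Table 2.** Pr(0) = 0.99^80 = 44.8%. Pr(1+) = 100 − 44.8 = 55.2%. Pr(2+) = 55.2 − 80 × 0.01 × 0.99^79 = 19.1%. Only the 5.2 is wrong, by a factor of 55.2/5.2 ≈ 10.6.

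**The case against.** The best reply is that the tables are largely sound. All of Tables 5 and 11 and three quarters of Table 12 follow from one standard approximation to Fisher's test. The approximation and the choice of Fisher over Barnard both err towards understating power. The SAP uses Tables 11 and 12 only to say that power is limited, which remains true: under Barnard, 10% versus about 64% is still needed for 80% power with 9 and 18. The 5.2 in Table 2 sits between two correct figures, the accompanying text for n = 80 (2.9%) is right, and a dropped digit could even come from the reading of the PDF. No sample size or analysis changes. All of this stands, and it limits the weight of the point.

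It does not rescue the three cells. A 90 in both the 10% and 20% rows is impossible under any one method; the 92 disagrees with the method behind its neighbours; and 5.2 contradicts its own row.

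A reader who enumerates Fisher's test might go further and infer that Tables 11 and 12 as a whole fail to reproduce, that the N/A in Table 11 is an error, and that the 90 should simply become 71. The document does not support that:

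- Section 8.5 names no test, and the approximation returns every cell of Table 11. For 30% versus 100% it gives 83.8% power, so N/A is right on that basis. Exact Fisher reaches 90.1% only at a true rate of exactly 100%.
- Most of the gap to exact Fisher is approximation against exact test, not faulty arithmetic.
- A lone 71 would fall below the 72 printed beside it for 80% power. It is right only if the whole table is recomputed.

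**Conclusion.** The point holds, at modest weight.

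- **Table 12:** the 10%/90%-power cell should be 80 on the table's apparent basis, 10 points below the printed 90 (about 71 under exact Fisher or Barnard). The 40%/80%-power cell should be 97, 5 points above the printed 92, unless the table is moved to an exact test.
- **Method:** Section 8.3 describes as Fisher's exact a set of figures that match an approximation and lie 1.2 to 2.9 points above exact Fisher. Section 8.5 names nothing. Section 9.4.1 uses Barnard's test, so the tables do not describe the planned analysis.
- **Table 2:** 5.2 should be 55.2.

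It would be wrong to infer that power is overstated overall. The approximation and the mismatch of tests are conservative, and so is the 90. The 92 is optimistic only against its neighbours' method; under Barnard 91 suffices. The statement of limited power is unaffected.

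Two assumptions matter. Tables 11 and 12 are taken to use a two-sided alpha of 0.05. The arcsine method is inferred from the match in 22 of 24 cells and is not stated in the SAP. It does not account for everything in Section 8.3: for 50% versus 100% the SAP quotes 97% power, against 98.5% by exact Fisher and 94.3% by the approximation (2·asin√0.9722 − 2·asin√0.5278 = 2.8067 − 1.6264 = 1.1803; 1.1803/0.3333 − 1.96 = 1.581). The verdict on the 10%/90%-power cell and on Table 2 does not depend on that inference.

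**What to change.** **Preferred.** Recompute Tables 5, 11 and 12 in full by exact enumeration for the two-sided Barnard test of Section 9.4.1, and name test and alpha in each caption. The entries (80%/90% power, rounded up) would be about:

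- Table 5: 52/58, 66/73, 77/83, 84/89, 91/95
- Table 11: 74/82, 85/91, 93/97
- Table 12: 64/71, 75/82, 84/90, 91/96

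Replace the sentence in Section 8.3 that names Fisher's test and re-derive the quoted 97% on the same basis.

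**Minimum.** In Table 12, change 90 to 80 (10% row, 90% power) and 92 to 97 (40% row, 80% power). State in Sections 8.3 and 8.5 that the figures are a normal approximation and that the analysis will use Barnard's test.

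**Either way.** In Table 2, 1% row, correct Pr(1+/80) to 55.2, after checking the source file in case the digit was lost in text extraction.

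Cost: about an hour of computation and a wording change to the SAP. Sample size, analyses and the limited-power conclusion stay as they are.

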9. STATISTICAL ANALYSIS

All data from enrolled participants will be analyzed according to the initial randomization assignment regardless of how many vaccinations they received. Analyses are modified intent-to-treat in that individuals who are randomized but not enrolled do not contribute data and hence are excluded. Because of blinding and the brief length of time between randomization and enrollment—typically no more than 4 working days—very few such individuals are expected.

No formal multiple comparison adjustments will be employed for multiple safety endpoints, multiple primary immunogenicity endpoints, or secondary endpoints. However, multiplicity adjustments will be made for certain immunogenicity assays, when the assay endpoint is viewed as a collection of hypotheses (e.g., testing multiple peptide pools to determine a positive response). Analyses will be performed using SAS and/or R.

